2.2.3 Preliminary Data

The proposed study builds upon the successful Jefferson/CIP research collaboration and the work completed through a prior Merck MISP-funded project. That project was a single group observational cohort study

testing the effect of the Pharmacists' Pneumonia Prevention Program (PPPP) on participant's vaccination knowledge, beliefs, and activation. In addition, as described above, an economic analysis was conducted to measure PPPP's intervention costs and to identify opportunities for increasing its efficiency.

[figure not shown]
PPPP was delivered to **203 older adults at predominantly African American senior centers and other community based venues** in
Philadelphia eight times in 2014, and consisted of: 1) a pharmacist-delivered
30 minute formal presentation, 2) a 10 minute culturally-sensitive live skit
performed by senior center actors, 3) small group action planning facilitated
by pharmacists, and 4) optional pneumococcal vaccination. Participants'
pneumonia and vaccination knowledge, beliefs, and activation were
measured at baseline, post-test, and 3 months.

Findings indicated that **PPPP significantly improved knowledge** of pneumococcal disease and immunization in an older, minority population using a novel senior center model of care. Specifically, there was a 54% increase in the total mean knowledge score among participants from baseline to 3 months. These findings are important because understanding pneumococcal disease and vaccination importance have consistently been linked to receipt of the vaccine ²⁰⁻²⁶

In addition, an increase in activation was observed among PPPP participants. More than one-third of participants who had not received the vaccination or had an unknown vaccination status at the start of the program stated that they received the vaccination as a result of PPPP participation. Participants also reported taking other activation steps including speaking with physicians and pharmacists about pneumococcal disease and vaccination as well as engaging in conversations with family members and friends about the topic.

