2.7.2 Definitions of Study Measures

Study measures will be assessed at baseline, immediately following the program ("posttest"), and 1 month after the program. The baseline and posttests will be administered in person on the date of the intervention. The 1 month follow up will be administered by phone (with up to 4 attempts to reach the participant). It should be noted that the team considered a more distal follow up point (i.e., at 2 or 3 months), but based on experience with the prior PPPP study felt that an earlier follow up would make it easier to reach participants with fewer call attempts. If the reviewers of this proposal conclude that 1 month is too soon for a follow up, we are willing to revise our plan to include a follow up at 2 or 3 months.

Knowledge and awareness of vaccine-preventable disease (Objective 1):

Knowledge and awareness about the target vaccine-preventable diseases will be assessed with a 15-20 item inventory encompassing the following domains: susceptibility to infection, symptoms of disease, severity of illness, and vaccination with an emphasis on vaccine efficacy, safety, and eligibility. These items will be selected following a review of the literature since no single validated instrument exists to assess knowledge of all three target diseases. ^{28,29,32,33,36-40}

Similar to the prior pneumonia project, **pneumonia knowledge** will be assessed using an instrument developed by our group using previously published literature. The prior instrument consisted of 6 "check all that apply" questions. Each item correctly checked was worth 1 point, for a maximum possible score of 28 points (see Figure 4 for a summary). We plan to retain the same instrument for the proposed study in order to enable comparison of pneumonia knowledge between the studies. However, we will also add a module pertaining to **zoster knowledge** which takes the same form as the established instrument.

Figure 4. Summary of Pneumonia Knowledge Instrument

Knowledge Assessment Questions	Maximum Number of Correct Responses Possible
Who is at risk of getting pneumonia?	9
How can you catch pneumonia from an infected person who is near you?	4
Which of these are symptoms of pneumococcal disease?	5

I should call my doctor or get emergency help if I get any of the following problems after vaccination:	5
Which of the following are possible side effects of the pneumonia vaccine?	5
TOTAL SCORE	28

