2.7.3 Sample Size Justification

The sample size was calculated using G*Power 3.0.10 and is based on the primary outcome measure (difference between change in mean knowledge score from baseline to 1 month for PHARM vs PEER). We plan to use a two-tailed independent samples t-test with α =0.05 to determine the between-group difference in mean knowledge scores at each timepoint. We seek to examine the difference, if any, in the effectiveness of the two approaches, PHARM and PEER; specifically, we wish to determine if the two approaches have similar results to within 20% difference expecting large variability (50% standard deviation). This difference is detectable at a power of 0.8 with 121 participants in each arm of the study. To ensure an adequate sample size, we scaled up the sample size calculation using the attrition rate from the prior pneumonia project. Attrition rate in PPPP was $\frac{203-143}{203}$ =0.296 ≈30%; thus scaling up by 30% yields a total sample size of 316 (158 in each arm).

As a secondary outcome, consistent with the prior pneumonia project, we plan to use a two-tailed paired samples t-test to determine the within-group difference in mean knowledge score between timepoints. However, because within-group differences are easier to detect than between-group differences, the sample size is powered to detect the 20% between-group difference.

2.8 Specific Drug Supply Requirements	None – vaccination is not included as a component of this study.	
2.9 Adverse Experience Reporting	Not required since vaccination is not being offered through this study.	
2.10 Itemized Study Budget	Provided as attachment.	

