TITLE: Randomized Trial of Peer-to-Peer Versus Pharmacist Education to

Improve Older Adults' Vaccination Knowledge Through the Senior Center Model of Care

CLINICALTRIALS.GOV

NCT NUMBER

NCT03239665

March 6, 2020 **DOCUMENT DATE:**

Overview of Statistical Analysis

The design of the study was a randomized trial with randomization to PHARM or PEER performed at the program date level. The primary outcome measure was a between-group comparison of change in knowledge for PHARM vs. PEER at BL vs. PT, and BL vs. M1. Secondary measures included between-group examinations of beliefs, trust, and activation at all 3 time points (BL vs. PT and M1). We also measured within-group differences in knowledge, beliefs, and activation and the intervention costs of PHARM and PEER, including program development, training and implementation.

Study data was recorded using paper forms and input into SAS Version 9.4 for analysis. Electronic data was password-protected by CIP while enrollment and data collection were ongoing. Files were checked to ensure de-identification prior to sharing with the Rutgers University investigators who completed the analyses.

Analysis was performed using an Intention-to-Treat (ITT) sample. This sample included all participants meeting study including criteria with ≥ 1 documented response from the baseline survey. In the case of missing data from the post-intervention or one-month follow-up survey, the matrix below was used to carry forward observations. For all tests, the significance level was chosen as $\alpha = 0.05$, and was downward adjusted via the Bonferroni method when appropriate.

Table 1. ITT approach for handling missing follow-up data.

BL Data	PT Data	M1 Data
Present	Present	Absent Utilize PT Data
Present	Absent	Present
	Utilize BL Data	
Present	Absent	Absent
	Utilize BL Data	Utilize BL Data

^{*}BL = baseline, PT = post-intervention, M1 = one-month follow-up

Baseline Demographics

Demographic analysis was carried out via t-test for continuous variables and Chi-square test for categorical variables.

Knowledge

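### The attrition allowance multiplies where it should divide, so 158 per arm leaves about 111 rather than 121; the 121 does not follow from the printed inputs, and the 0.8 was not computed for the SAP's primary analysis

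*Protocol*

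**What the plan says.** Protocol section 2.7.3 sizes the trial on one primary measure, the "difference between change in mean knowledge score from baseline to 1 month for PHARM vs PEER". The planned test is a two-tailed independent-samples t-test at α = 0.05, used "to determine the between-group difference in mean knowledge scores at each timepoint". The aim is to see whether the two programs give "similar results to within 20% difference expecting large variability (50% standard deviation"). The section then says: "This difference is detectable at a power of 0.8 with 121 participants in each arm of the study". Attrition in the prior pneumonia project was (203 − 143)/203 = 0.296, rounded to 30%, and the section concludes: "thus scaling up by 30% yields a total sample size of 316 (158 in each arm").

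The SAP overview names two primary between-group contrasts of change in knowledge: baseline to post-test and baseline to 1 month. It analyses everyone eligible with at least one baseline response and carries earlier values forward when later ones are missing. Its Knowledge section tests between-group differences across timepoints by Wilcoxon rank-sum at 0.05/3 = 0.0167. The SAP gives no sample size or power.

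**The concern.** Power of 0.8 is the only support the documents give for the trial's size, and three things about it do not fit together. The allowance for loss does not return the 121 it was meant to protect. The 121 cannot be obtained from the effect size, SD and alpha printed beside it. And the contrast, test, threshold and analysis set to which the 0.8 belongs are not those in the SAP.

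The primary hypothesis expects similar improvement in the two arms, so a non-significant comparison is the expected result. A reader will weigh that result against the stated power, and should be able to tell what the figure refers to.

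**Working it through.** **Inputs, from protocol section 2.7.3 unless noted.** Difference 20%; SD 50%; two-sided t-test; α = 0.05; power 0.8; 121 evaluable per arm; attrition 60/203 ≈ 30%; 158 enrolled per arm. From the SAP: threshold 0.05/3 = 0.0167. All power figures use the noncentral t distribution with equal arms, and all ignore clustering.

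**1. Reproduce the 158.** 121 × 1.30 = 157.3, rounded up to 158. This matches the protocol.

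**2. Apply the protocol's attrition to it.**
- 158 × 0.70 = 110.6; at the unrounded rate, 158 × 143/203 = 111.3. So about 111 per arm have 1-month data, 10 short of 121.
- Enrolment that retains 121: 121/(1 − 0.30) = 172.9, so 173 per arm.
- Largest loss at which 158 still retains 121: 1 − 121/158 = 0.234, or 23.4%.

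**3. Try to reproduce the 121.**
- Printed inputs: d = 20/50 = 0.40, two-sided 0.05, power 0.8. Required n = 99.08, so 100 per arm. This does not match.
- Two sets of inputs that would match, neither of them stated:
  - d = 0.40 at α = 0.025: n = 120.08, so 121.
  - SD taken as 50% of each arm's own mean, with means in the ratio 1 to 1.2: d = 0.2/√((0.5² + 0.6²)/2) = 0.362. At α = 0.05, n = 120.66, so 121.
- These are back-solved examples. Others may exist, and the text does not show which, if any, was used.

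**4. Power at 111 completers per arm, against the protocol's own target.**

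| Inputs | n per arm for 0.8 | Power at 111 |
|---|---|---|
| d = 0.40, α = 0.05 (as printed) | 100 | 0.84 |
| d = 0.40, α = 0.025 (example) | 121 | 0.765 |
| d = 0.362, α = 0.05 (example) | 121 | 0.766 |

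**5. Compare the sized analysis with the SAP's.**

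| | Protocol 2.7.3 | SAP |
|---|---|---|
| Primary contrast | Baseline to 1 month | Baseline to post-test; baseline to 1 month |
| Test | t-test | Wilcoxon rank-sum |
| Threshold | 0.05 | 0.0167 |
| Number analysed | 121 evaluable per arm | All with a baseline response, carried forward; up to 158 per arm |
| Power stated | 0.8 | None |

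The nearest simple figure for the SAP's own set is a t-test approximation with 158 per arm at 0.0167: 0.87 for d = 0.40, and 0.79 for d = 0.362. It assumes that carry-forward changes neither the effect nor the SD, and that there is no clustering. The SAP's table fills a missing 1-month value with the baseline value when the post-test is also missing. That participant then counts as zero change, so the first assumption is not assured.

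**The case against.** The strongest reply is that little follows from the slip. On the inputs the protocol prints, 100 per arm is enough, so 111 completers still exceed the need. Loss may also be below 30%: the prior project was "measured at baseline, post-test, and 3 months", whereas this trial calls at 1 month because the team "felt that an earlier follow up would make it easier to reach participants with fewer call attempts". Moreover, the post-test is taken on the day of the program, so follow-up loss bears mainly on the 1-month contrast, and the SAP's carry-forward rule keeps participants in the analysis. All of this stands, and it is why the point is minor. It does not make the arithmetic right at the rate the protocol chose to plan with, and it does not explain the 121.

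Three stronger readings are tempting and are not supported.

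- A reader might infer that attrition takes the trial below 0.8 on its stated design. It does not: the printed inputs give 0.84 at 111.
- A reader might combine 111 completers with the 0.0167 threshold and report power of 0.61 to 0.71 (d = 0.362 to d = 0.40). That pairs the protocol's completers with a threshold the SAP applies to a carry-forward set of up to 158 per arm. Neither document plans that analysis.
- A reader might add that the rank-sum test lowers power a little further. That holds for normal data, but the SAP chose the test because it expected non-normal, integer-valued scores, and with such data the direction can reverse.

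It is also fair to say that no design-stage power figure turns a non-significant difference into evidence of similarity. That is a separate matter, and this correction does not settle it.

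**Conclusion.** The point holds, at minor severity. The attrition step is wrong as written: at 30% loss, 158 per arm gives about 111 with 1-month data, and 173 would have been needed to keep 121. The 121 does not follow from the printed inputs, which give 100. Power at 111 is 0.84 on those inputs, and about 0.77 if 121 was the true requirement. The stated 0.8 belongs to a single contrast, test, threshold and evaluable set that differ from the SAP's, and no power is given for the SAP's analysis.

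The attrition arithmetic needs no assumption beyond the protocol's own 30%. The power figures assume independent observations. The SAP describes "randomization to PHARM or PEER performed at the program date level", and any positive correlation within a program date would lower all of them. The documents give no intraclass correlation, so this is not quantified here.

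**What to change.** Issue a dated correction note. No added enrolment is asked for.

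- **Protocol 2.7.3, inputs.** State the G*Power entries behind 121 (effect size, basis of the SD, alpha). If they are no longer held, say so, and say that the printed inputs give 100 per arm. Do not offer a back-solved set as the one that was used.
- **Protocol 2.7.3, attrition.** Say that 158 per arm yields about 111 completers at 30% loss and that 173 would have retained 121. Restate power at 111 as 0.84 on the printed inputs, or about 0.77 if 121 was the true requirement, noting in the same sentence that clustering by program date is ignored.
- **SAP overview.** Disclose that the protocol's 0.8 does not apply to the SAP's contrasts, test, threshold and analysis set, and identify baseline to 1 month as the contrast the trial was sized on. If a figure at 0.0167 is wanted, give the t-test approximation for the SAP's own set: 0.87 at up to 158 per arm for d = 0.40 (0.79 for d = 0.362), labelled as an upper bound that assumes no dilution from carry-forward and no clustering.

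The cost is a paragraph in each document and a search for the G*Power record. The downside is that the stated power becomes less favourable or less certain, and the difference between the protocol's and the SAP's primary analyses becomes visible.

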2.13 Protocol Submission for Investigator- Initiated Studies	U.S. protocols should be submitted by US investigators directly or through the Global Research Specialist at www.merckiisp.com Non U.S. protocols should be submitted to the MSD office by the investigators.	

Appendix. Results of a Local Needs Assessment on Zoster

Because little was known about the local need specific to zoster vaccination, a survey was fielded to 58 older adults at CIP in 2015. The instrument consisted of 20 Likert Scale items assessing knowledge and perceptions of the zoster vaccine. Responses to selected Likert items are provided in Table 1.

The results demonstrate that there is uncertainty regarding the efficacy of the zoster vaccine, with less than 50% of individuals agreeing that the vaccine can prevent shingles. Additionally, many participants were unsure whether or not their physician or pharmacist thought that a zoster vaccine was important for them. They were also unsure about whether they would want a zoster vaccine if they were eligible or if they would recommend the vaccine to another.

Table 1. Key Results from Likert Items in the CIP Member Survey on Zoster Vaccination

Survey Item	Results
"The shingles shot keeps a person from getting shingles"	28/58 (48.3%) responded "completely agree" or "somewhat agree"
	30/58 (51.7%) responded "somewhat disagree," "completely disagree," or "unsure/I don't know"
"My doctor thinks it is important for me to get the shingles shot"	31/58 (53.4%) responded "completely agree" or "somewhat agree"
	27/58 (46.6%) responded "somewhat disagree," "completely disagree," or "unsure/I don't know"
"My pharmacist thinks it is important for me to get the shingles shot"	25/58 (43.1%) responded "completely agree" or "somewhat agree"
	33/58 (56.9%) responded "somewhat disagree," "completely disagree," or "unsure/I don't know"
"If I am eligible, I would want to get the shingles shot"	29/58 (50%) responded "completely agree" or "somewhat agree"
	29/58 (50%) responded "somewhat disagree," "completely disagree," or "unsure/I don't know"
"If my friend/family was eligible, I would encourage them to get a shingles shot"	31/58 (53.4%) responded "completely agree" or "somewhat agree"
	27/58 (46.6%) responded "somewhat disagree," "completely disagree," or "unsure/I don't know"
"It would be easy for me to get a shingles shot if I wanted one"	40 (69%) responded "completely agree" or "somewhat agree"
	18 (31%) responded "somewhat disagree," "completely disagree," or "unsure/I don't know"

A second key finding from the CIP member survey is that while many believed that it would be easy to get a zoster vaccine if they wanted one, nearly one-third either disagreed with this statement or were unsure if they would be able to get the vaccine. This finding also represents an opportunity for our program to provide access to the vaccine if participants are eligible.

The uncertainties uncovered in this survey represent opportunities for our program to **address these gaps** by educating this population on zoster vaccine efficacy as well as develop skills to engage their physicians and pharmacists in discussions about zoster and determine their vaccine eligibility.

TITLE: Randomized Trial of Peer-to-Peer Versus Pharmacist Education to

Improve Older Adults' Vaccination Knowledge Through the Senior Center Model of Care

CLINICALTRIALS.GOV

NCT NUMBER

NCT03239665

March 6, 2020 **DOCUMENT DATE:**

Overview of Statistical Analysis

The design of the study was a randomized trial with randomization to PHARM or PEER performed at the program date level. The primary outcome measure was a between-group comparison of change in knowledge for PHARM vs. PEER at BL vs. PT, and BL vs. M1. Secondary measures included between-group examinations of beliefs, trust, and activation at all 3 time points (BL vs. PT and M1). We also measured within-group differences in knowledge, beliefs, and activation and the intervention costs of PHARM and PEER, including program development, training and implementation.

Study data was recorded using paper forms and input into SAS Version 9.4 for analysis. Electronic data was password-protected by CIP while enrollment and data collection were ongoing. Files were checked to ensure de-identification prior to sharing with the Rutgers University investigators who completed the analyses.

Analysis was performed using an Intention-to-Treat (ITT) sample. This sample included all participants meeting study including criteria with ≥ 1 documented response from the baseline survey. In the case of missing data from the post-intervention or one-month follow-up survey, the matrix below was used to carry forward observations. For all tests, the significance level was chosen as $\alpha = 0.05$, and was downward adjusted via the Bonferroni method when appropriate.

Table 1. ITT approach for handling missing follow-up data.

BL Data	PT Data	M1 Data
Present	Present	Absent Utilize PT Data
Present	Absent	Present
	Utilize BL Data	
Present	Absent	Absent
	Utilize BL Data	Utilize BL Data

^{*}BL = baseline, PT = post-intervention, M1 = one-month follow-up

Baseline Demographics

Demographic analysis was carried out via t-test for continuous variables and Chi-square test for categorical variables.

Knowledge

The number of correct responses to the knowledge items at each timepoint was calculated as a whole and by disease (pneumonia, influenza, zoster). Baseline knowledge was compared by race via Kruskal-Wallis test. Because the knowledge data were expected to be non-normal and integer-valued, knowledge items were assessed using nonparametric methods. Specifically, between-group differences in knowledge were assessed at each timepoint via Wilcoxon Rank-Sum test. Similarly, between-group knowledge differences across timepoints were assessed pairwise via Wilcoxon Rank-Sum tests with Bonferroni-corrected significance threshold of

 α =0.05/3=0.0167. Within-group differences in knowledge score across timepoints were tested pairwise using Wilcoxon Signed-Rank tests.

Beliefs

The percentage of respondents answering "Completely Agree" to each item at each timepoint was calculated and compared between PHARM and PEER, as in our PPPP study. Pairwise Wilcoxon Signed-Rank tests were run comparing within-group changes in beliefs across timepoints applying Bonferroni correction (α =0.05/3=0.0167). Either Chi-Square or Fisher's Exact tests were used to compare beliefs between groups at each timepoint, depending on expected cell counts.

Activation

For all participants, Chi-Square or Fisher's Exact testing was performed as appropriate at each timepoint to assess between-group differences in proportions of participants planning actions, including planning vaccination and planning to speak with a doctor, pharmacist, or family/friends, as well as actions taken, including vaccinations obtained and having spoken with a doctor, pharmacist, or family/friends.

For participants who did not report positive vaccination status on the post-intervention survey, Chi-Square or Fisher's Exact testing was performed on PT & M1 data for each vaccine type to test for differences between PHARM and PEER with significance level α =0.05. The PT response to the vaccination items was chosen instead of the BL response because it was felt that the responses to these items would be more reliable and accurate after having received the intervention as compared to baseline, when participants may have had a less clear ability to differentiate between the vaccines they may have received. For survey items pertaining to plans/actions related to vaccines, participants not reporting positive vaccination status were compared between PHARM and PEER at each timepoint for item (discussion with doctor, pharmacist, or family/friends) via Chi-Square or Fisher's Exact tests as appropriate.

Satisfaction

For both PT and M1, proportions of respondents answering favorably ("Completely Agree" or "Somewhat Agree") and unfavorably ("Completely Disagree" or "Somewhat Disagree") to the two satisfaction items (program satisfaction and program engagement) were compared between PHARM and PEER using either Chi-Square or Fisher's Exact test as appropriate.

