2.5 Study Procedures

Inclusion criteria are 1) Age \geq 50; 2) can attend a 2-hour session (though both PHARM and PEER entail 60 minutes of intervention, an additional hour is needed to allow for informed consent and data collection); 3) speak and read English at \geq 4th grade level as determined by a brief reading passage; 4) cognitively intact as evidenced by an Abbreviated Mental Status Test score \geq 7.

The study will consist of two arms designed to educate participants about vaccine-preventable disease and vaccination: 1) PHARM will consist of a 60-minute didactic lecture delivered by a pharmacist and video clips pertaining to 3 vaccine-preventable diseases (zoster, pneumonia, and influenza), and 2) a peer-led intervention ("PEER") will consist of a 60 minute small-group session including roleplaying exercises on these three vaccine-preventable diseases. The components of these interventions will be designed to address specific barriers in our framework. The interventions will focus on pneumococcal disease and zoster but will include limited content on influenza because participants are likely to have questions about how the flu and its vaccination differ from pneumococcal diseases and zoster.

Because the primary goal of the program is participant education, vaccination will not be included as a component of the program. As noted, vaccine costs in our prior study were high, representing nearly a quarter of total program cost. In addition, only 10% of participants opted to get vaccinated through that program (though many reported receiving the pneumonia vaccination through other avenues, for example physician's office or community pharmacy). For the proposed study, both PHARM and PEER groups will receive a listing of local vaccination sites, including clinics and pharmacies within a 3 mile radius of the program location.

PEER will be delivered by 10 peer educators, each leading small groups of 5-6 participants, for a total of 158 PEER participants. **PHARM** will be

delivered to 3 groups of 50-55 participants, or possibly 6 groups of 25-30 participants for a total of 158 PHARM participants.

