Delivery of the PEER Intervention: PEER will be run over a 60-minute session. On the day of the PEER program, participants will breakout into assigned small groups. During this session, peer educators will deliver the skit and complete the role play exercises. Participants will then be asked what key points they learned about vaccine-preventable diseases and vaccines. Finally, the peer educator will engage in a dialogue to clarify and summarize these key points.

Summary of PHARM and PEER Interventions and Procedures

A summary of the PHARM and PEER interventions and procedures is provided below.

Figure 3. Summary of Interventions and Procedures

Study data will be recorded using paper forms and input into IBM SPSS for analysis. Electronic data will be password-protected by CIP while enrollment and data collection are ongoing. Files will be checked to ensure deidentification prior to sharing with the Rutgers investigators who will complete the analyses.

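### Program dates were randomised, but the sample size and every between-arm test treat participants as independent, so with any positive within-date correlation the between-arm p-values are, on average, too small.

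*SAP*

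**What the plan says.** The SAP (Overview of Statistical Analysis) defines the allocation: "The design of the study was a randomized trial with randomization to PHARM or PEER performed at the program date level".

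Delivery was planned in shared sessions. Protocol section 2.5 has PHARM "delivered to 3 groups of 50-55 participants, or possibly 6 groups of 25-30 participants". PEER has 10 educators, each leading groups of 5 to 6, and section 2.5.2 adds: "On the day of the PEER program, participants will breakout into assigned small groups". PEER therefore has a second layer of grouping within the date.

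Section 2.7.3 sizes the trial with a two-sided independent-samples t-test at alpha 0.05, for a 20% difference with a 50% standard deviation: "This difference is detectable at a power of 0.8 with 121 participants in each arm of the study". The only inflation is for loss to follow-up: "we scaled up the sample size calculation using the attrition rate from the prior pneumonia project". This gives 158 per arm.

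The SAP's between-arm tests are all at participant level. For change in knowledge, "between-group knowledge differences across timepoints were assessed pairwise via Wilcoxon Rank-Sum tests with Bonferroni-corrected significance threshold of" 0.0167. Knowledge at each timepoint also uses the rank-sum test. Beliefs and activation use chi-square or Fisher tests. Satisfaction proportions "were compared between PHARM and PEER using either Chi-Square or Fisher's Exact test as appropriate".

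**The concern.** A rank-sum, chi-square or Fisher test gets its null distribution by treating each participant as separately allocated. Here whole dates were allocated. If people at one date resemble each other more than people at different dates (same presenter or educators, same discussion, same community group), each extra attendee adds less information than these tests assume. The standard error is then too small.

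Two things are at stake. First, a between-arm difference may be declared at well above the stated error rate. Second, the primary hypothesis (protocol 2.1.1) is that the arms improve similarly. A participant-level confidence interval offered in support of that would be too narrow.

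No cluster term, date-level summary, robust variance, design effect, ICC or count of dates appears in the available text of either document. The within-arm tests and the comparison of baseline knowledge by race are outside this point.

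**Working it through.** **The plan's own figure.** With d = 20/50 = 0.4, two-sided alpha 0.05 and independent participants, the t-test needs about 100 per arm for power 0.80. At 121 per arm its power is 0.87, and at 158 it is 0.94. So 121 does not reproduce from the stated inputs. The excess over 100 would offset a design effect of only 121/100 = 1.21, it is not presented as a clustering allowance, and it does nothing for type I error. The step from 121 to 158 is 121 × 1.3 = 157.3, rounded up, for attrition alone.

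**Assumptions not in the documents.** ICC of 0.01, 0.02 or 0.05; 3 or 6 dates per arm, borrowed from the two PHARM group options because PEER dates are not stated; equal-sized dates.

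**Design effect and type I error** at 158 per arm. DEFF = 1 + (m − 1) × ICC, with m = 158/3 = 52.7 or 158/6 = 26.3. Effective n = 158/DEFF. True error = 2 × [1 − Φ(z/√DEFF)], with z = 1.960 for 0.05 and 2.394 for 0.0167. Example: 3 dates, ICC 0.01 gives DEFF = 1 + 51.7 × 0.01 = 1.52; 2.394/√1.52 = 1.94; error 0.052.

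| Dates per arm | ICC | DEFF | Effective n per arm | True error at 0.05 | True error at 0.0167 |
|---|---|---|---|---|---|
| 3 | 0.01 | 1.52 | 104 | 0.11 | 0.05 |
| 3 | 0.02 | 2.03 | 78 | 0.17 | 0.09 |
| 3 | 0.05 | 3.58 | 44 | 0.30 | 0.21 |
| 6 | 0.01 | 1.25 | 126 | 0.08 | 0.03 |
| 6 | 0.02 | 1.51 | 105 | 0.11 | 0.05 |
| 6 | 0.05 | 2.27 | 70 | 0.19 | 0.11 |

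With 6 dates against 3, averaging the two arms' design effects gives 0.10 to 0.25 at 0.05 and 0.04 to 0.16 at 0.0167. Simulated rank-sum tests (20,000 null trials per cell, continuous and integer scores) agree with these figures. At ICC 0 they return 0.049 to 0.051 and 0.015 to 0.018, as they should.

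**Interval width.** Participant-level standard errors are understated by √DEFF: a factor of 1.23 to 1.89 with 3 dates per arm and 1.12 to 1.51 with 6.

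**Power of a valid date-level t-test** at d = 0.4. The variance of an arm mean is (ICC + (1 − ICC)/m)/k for k dates, in SD units; df = kA + kB − 2; noncentral t. Example: 3 v 3, ICC 0.01, 158 per arm: (0.01 + 0.99/52.7)/3 = 0.0096; noncentrality 0.4/√0.0192 = 2.89 on 4 df; power 0.59.

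| Dates (A v B) | ICC 0, 158 per arm | ICC 0.01 to 0.05, 158 per arm | ICC 0.01 to 0.05, 121 per arm |
|---|---|---|---|
| 3 v 3 | 0.76 | 0.59 to 0.30 | 0.52 to 0.29 |
| 6 v 3 | 0.86 | 0.74 to 0.43 | 0.65 to 0.40 |
| 6 v 6 | 0.89 | 0.82 to 0.57 | 0.73 to 0.52 |

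The tabulated powers use alpha 0.05. At the 0.0167 threshold with 158 per arm they fall to 0.32 to 0.13 (3 v 3) or 0.63 to 0.36 (6 v 6). The ICC 0 column shows that part of the loss comes from few degrees of freedom and not from correlation.

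**The case against.** The mismatch itself is not in dispute; its size and certainty are.

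- **Average, not every result.** Clustering inflates the error rate; it does not make each realised p-value too small. This stands, and the conclusion is worded that way.
- **Change scores.** Stable differences between audiences cancel in change from baseline, so the relevant ICC may be lower than that of raw scores. This stands as a reason for a modest ICC. It does not remove variation arising in the session, which everyone present shares.
- **Date counts.** PHARM groups are not stated to be dates, the dates may have been paired or blocked, and parts of the protocol are missing from the text available. More dates would be milder: with 10 per arm and the same ICC range, the error is 0.07 to 0.14 at 0.05 and 0.025 to 0.07 at 0.0167, with date-level power 0.88 to 0.72 (158 per arm, alpha 0.05). The inflation shrinks but remains.
- **Direction of the hypothesis.** False positives work against a claim of similarity, and correction would generally not overturn a non-significant result. That is fair, but the understated interval width still matters for such a claim.
- **Sample size.** Only the SAP states date-level allocation, and the size can no longer be changed. This stands: section 2.7.3 calls for a reporting caveat, not a redesign.

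Bonferroni adjustment deals with multiple comparisons, and rank tests relax normality. Neither deals with dependence.

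**Conclusion.** The concern holds. Allocation was by date, and the sample size and all described between-arm tests assume independent participants, including the primary knowledge comparison. The direction is certain for any positive within-date correlation; the size is not, because the ICC and the number of dates are not given.

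For the assumed range, type I error at the 0.0167 threshold is roughly two to twelve times nominal across the 3- and 6-date cases (0.03 to 0.21). Date-level power at alpha 0.05 falls below 0.80 in every tabulated case with positive ICC except the mildest (6 v 6, ICC 0.01, 158 per arm: 0.82).

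**What to change.** 1. Report the number of program dates per arm, participants per date, and any pairing or blocking of dates.
2. Make the primary between-arm knowledge analysis account for date. Name one of these as primary: a baseline-adjusted comparison of date-level means, or a mixed model with a random intercept for date, baseline knowledge as covariate and small-sample degrees of freedom. With as few as six dates in total, the first is less fragile. Reflect any pairing or blocking, and allow for PEER educator or small group where recorded.
3. Because the SAP expects non-normal integer scores, add a date-level permutation test. Its smallest two-sided p-value is 2/C(6,3) = 2/20 = 0.10 with 3 v 3 dates, so it could not reach 0.0167; with 6 v 6 it is 2/C(12,6) = 2/924 = 0.002.
4. For beliefs, activation and satisfaction, use date-level proportions or GEE with a small-sample correction.
5. Report the estimated ICC and the achieved confidence interval, and state that the power in section 2.7.3 assumed independence.
6. If no date code can be recovered, label the present p-values as unadjusted for clustering and show each with z divided by √DEFF over a range of ICCs. For example, p = 0.0167 becomes 0.05 to 0.21 with 3 dates per arm, or 0.03 to 0.11 with 6.

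**Cost.** SAP wording and a re-run, if an anonymous date code is in the analysis file or can be added. The SAP says "Files were checked to ensure de-identification prior to sharing with the Rutgers University investigators who completed the analyses" but not whether such a code was kept, so this must be confirmed. The results will have wider intervals, few degrees of freedom and lower stated power, and a nominally significant between-arm difference may no longer be significant.
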